5.2 Definition of Baseline

The baseline value must be assessed prior to initiation of study treatment. For Hb, baseline will be calculated as an average of the last 2 values prior to or on the first dose date, as specified in [Section 9.2.1](#). For other parameters, unless otherwise specified, baseline will be defined as the last available value prior to the first dose of IMP.

5.3 Prior and Concomitant Medication

Prior medication is defined as any medications taken before the date of the first dose of IMP. Concomitant medication is defined as any medications taken at any time from the date of the first dose of IMP through the date of the last dose of the IMP.

Prior and concomitant medications will be coded using World Health Organization Drug dictionary and summarized for each treatment group based on the safety population. Prior and concomitant ESA medications and their reasons of usage will be summarized by treatment group. Number of subjects taking concomitant anti-hypertensive medications, and number of concomitant anti-hypertensive medications taken will be summarized by study period for each treatment group as well.

5.4 Handling of Missing Data

Missing data will be handled using a procedure specific to each variable and analysis as described in the sections relevant to each endpoint. If no method for missing data is discussed, descriptive analyses will be based upon observed data without imputation.

For the analysis of safety variables, only partial dates will be imputed unless otherwise specified. The algorithms for imputation of partial dates depend upon the parameter, as follows.

Adverse event onset

- If onset date is completely missing, date is set to date of first dose.
- If year is present and month and day are missing, or year and day are present, but month is missing:
 - If year = year of first dose, then set month and day to month and day of first dose.
 - If year < year of first dose, then set month and day to December 31.
 - If year > year of first dose, then set month and day to January 1.
- If month and year are present and day is missing:

- If year = year of first dose and
 - month = month of first dose, then set day to day of first dose date.
 - month < month of first dose, then set day to last day of month.
 - month > month of first dose, then set day to first day of month.
- If year < year of first dose, then set day to last day of month.
- If year > year of first dose, then set day to first day of month.
- For all other cases, set date to date of first dose.

Adverse event end date

- If year is present and month and day are missing, or year and day are present and month is missing, set end month and day to December 31.
- If month and year are present and day is missing, set the day to last day of the month.
- If fatal event, date is set to minimum of imputed end date and death date.
- For all other cases, set date to missing.

Concomitant medication

- If start date is completely missing, start date will not be imputed.
- If start year is present and month and day are missing, or year and day are present and month is missing, set start month and day to January 1.
- If start year and month are present and day is missing, set start day to 1st day of month.
- If end date is completely missing, end date will not be imputed.
- If end year is present and month and day are missing, or year and day are present and month is missing, set end month and day to December 31.
- If end year and month are present and day is missing, set end day to last day of the month.
- The imputed dates must be logical, ensuring that no end date is after database lock or death or before the start date.

If site queries fail to resolve partial dates for laboratory values and vital signs, including for efficacy, the date is missing and will not be imputed.

6 Efficacy Endpoints

This section lists the efficacy endpoints; [Section 9](#) describes their definitions and the plans for the analysis of each endpoint.

6.1 Primary Efficacy Endpoint

The primary efficacy endpoint is the change in Hb between Baseline (average pretreatment Hb) and the primary evaluation period (average Hb from Weeks 20 to 26, inclusive).

6.2 Key Secondary Efficacy Endpoints

The key secondary efficacy endpoint is the change in Hb between Baseline and the secondary evaluation period (average Hb from Weeks 46 to 52).

6.3 Other Efficacy Endpoints

Other efficacy endpoints include the following:

- Proportion of subjects having average Hb values within the target range during the primary evaluation period (Weeks 20 to 26).
- Proportion of subjects having average Hb values within the target range during the secondary evaluation period (Weeks 46 to 52).
- Proportion of subjects receiving intravenous (IV) iron therapy from Baseline to Week 52.
- Average weekly dose of IV elemental iron administered from Baseline to Week 52 in subjects who have received IV elemental iron.
- Receipt of ESA rescue.
- Proportion of subjects receiving red blood cell (RBC) transfusions from Baseline to Week 26.
- Proportion of subjects receiving RBC transfusions from Baseline to Week 52.
- Change from baseline in 36-Item Short Form Version 2 (SF-36v2) Health-Related Quality of Life (HRQOL) scores.
- Change from baseline to the average value in Anemia Subscale ("Additional Concerns") of Functional Assessment of Cancer Therapy-Anemia (FACT-An) Score.
- Change from baseline to the average value in Total FACT-An Score.
- Change from baseline in score of Patient Global Impression of Severity (PGI-S).
- Score of Patient Global Impression of Change (PGI-C).

6.4 Rescue Therapy

The narrow and broad-on-treatment rescue therapies are defined as follows:

- Narrow: For all treatment arms, narrow rescue therapy is defined as rescue for worsening anemia with ESA medication or RBC transfusion, not starting after permanent study treatment discontinuation. Reason includes "Hb <9.5 g/dL". For

darbepoetin alfa arm, darbepoetin alfa with increases in dose $\geq 50\%$ or $\geq 100\%$ will be considered as ESA rescue medication.

- Broad-on-treatment: For all treatment arms, broad-on-treatment rescue therapy is defined as any exposure to ESA medication (aside from darbepoetin alfa not designated as rescue in the control arm) or RBC transfusion for any reason not starting after permanent study treatment discontinuation. For darbepoetin alfa arm, darbepoetin alfa with increases in dose $\geq 50\%$ or $\geq 100\%$ will be considered as ESA rescue medication.

Reasons for ESA medication and RBC transfusion will be collected in eCRF. If a given therapy starts the same day as permanent discontinuation of study drug, then that therapy will be considered on treatment for rescue definitions.

In vadadustat arms, any use of ESA may be considered rescue. In darbepoetin alfa arm, since the study drug itself is an ESA, the use of another ESA may be considered rescue, and the increase dose in darbepoetin alfa may be planned titration or a rescue. Subjects treated darbepoetin alfa with increases in dose relative to last dose by percentage of $<50\%$, $\geq 50\%$ and $<100\%$, and $\geq 100\%$. Darbepoetin alfa treatment with $\geq 50\%$ or $\geq 100\%$ dose increases from last dose will be considered as rescue therapies. Subjects will be presented by their maximum category of increase within each of the five analysis time periods (see [Section 5.1](#)).

The time to the first ESA medication or RBC transfusion (narrow or broad-on-treatment therapy with $\geq 50\%$ or $\geq 100\%$ dose increase in darbepoetin alfa) will be analyzed by Cox regression model for treatment comparison in the randomized population. The estimated hazard ratio and its 95% CI will be performed. Kaplan-Meier curve will be displayed as well.

Analyzing the impact of pre-baseline or post-baseline ESA on vadadustat efficacy requires conversion of ESA dose into common units. The epoetin alfa analogues, darbepoetin alfa and methoxy polyethylene glycol epoetin beta (Mircera), will be converted to IV epoetin equivalent units per kilogram per week (U/kg/week). The following conversions have been derived from published literature and input from clinical experts [[Paganini, 1995](#); [Kaufman, 1998](#); [Cremieux, 2006](#); [Gosselin, 2006](#); [Levin, 2008](#); [FDA, 2011](#); [Jordan, 2012](#); [Choi, 2013](#); [Vega, 2014](#); [Wright, 2015](#)]:

Table 2. ESA Unit Conversion

	SC Epoetin	IV Epoetin
Darbepoetin alfa to epoetin	1:160	1:200
Methoxy polyethylene glycol-epoetin beta to epoetin	1:176	1:220

Subcutaneous (SC) epoetin to intravenous (IV) epoetin is 1:1.25.

7 Safety Endpoints

The following safety endpoints will be summarized by treatment groups:

- Adverse events (AEs) and serious adverse events (SAEs).
- Treatment-emergent adverse events (TEAEs) and treatment-emergent SAEs.
- Adverse events of special interest (AESI).
- Vital signs, ECGs and clinical laboratory values.
- Episodes of Hb >11.0 g/dL for US, > 12.0 g/dL, > 13.0 g/dL, > 14.0 g/dL, < 8.0 g/dL, or < 9.0 g/dL.
- Number of episodes of Hb increase > 1.0 g/dL within any 2-week interval or > 2.0 g/dL within any 4-week interval.

8 Pharmacokinetic (PK)/ Pharmacodynamic (PD)/ Pharmacogenomic (PGx) Analysis

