- Low darbepoetin alfa dose group ( $\leq 0.45 \text{ } \mu\text{g/kg/week}$ ): vadadustat 300 mg QD, 600 mg TIW.
- High darbepoetin alfa dose group ( $> 0.45 \text{ and } \leq 1.5 \text{ } \mu\text{g/kg/week}$ ): vadadustat 450 mg QD, 750 mg TIW.

Refer to the trial-specific Dosing Guideline for instructions on ESA medications conversion to an equivalent darbepoetin alfa dose for stratification and randomization.

Adjustments to doses for vadadustat will be guided by Hb concentration and Dose Adjustment Algorithms ([Section 6.1.1](#)).

For subjects who were receiving darbepoetin alfa during screening and randomized to the darbepoetin alfa treatment arm, the initial dosing regimen in the trial (starting from Baseline/Day 1) will be approximately the same weekly dose that they were receiving prior to randomization. Darbepoetin alfa dose will be administered IV at the hemodialysis clinic. For subjects receiving darbepoetin alfa for the first time, the initial dosing regimen (starting from Baseline/Day 1) will be determined by the US Package Insert (USPI) or European Union (EU) Summary of Product Characteristics (SmPC), per the medical

judgement of the investigator. Dose adjustments will be guided by the USPI or EU SmPC ([Section 6.1.1.4](#)). ESA dosing is independent of the visit schedule, and the dosing schedule may shift per local standard of care and investigator discretion.

Investigators will prescribe iron supplementation (IV, oral, or intradialytic) as needed during the trial to maintain ferritin  $\geq 100$  ng/mL or transferrin saturation (TSAT)  $\geq 20\%$  (see [Section 6.5.2.1](#) for details regarding iron supplementation during the trial). Subjects already receiving oral iron supplementation as part of their treatment plan may continue their current treatment regimen. Because of the potential for oral iron to reduce the bioavailability of vadadustat, the IMP is not to be administered concurrently with an oral iron supplement (including multivitamins containing iron), iron containing phosphate binders, or any oral medications containing iron.

Subjects will be instructed to take vadadustat at least 1 hour before oral medications containing iron ([Section 6.5.2.1](#)).

Clinical and safety assessments will be performed as indicated at Screening, during the Conversion and Maintenance Period, and during the Follow-up Period (4 weeks after the EOT) as shown in the Schedule of Assessments ([Table 1.3-1](#)).

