### **7.3.1 Treatment Interruption**

Subjects who temporarily interrupt IMP (vadadustat or darbepoetin alfa) treatment after the first dose and prior to completion of the trial will continue with trial visits and assessments. Unless contraindicated, treatment with IMP should be resumed within a 30-day time period from the start date of interruption and routinely considered at every visit following IMP interruption. If a subject does not return for a scheduled visit, every effort should be made to contact the subject.

During the trial, a subject may interrupt the IMP (vadadustat or darbepoetin alfa) for any of the following reasons:

- Adverse event.
- Missed dialysis visit (darbepoetin alfa arm).
- Investigator's discretion.
- Rapid rise in Hb (defined as  $> 1.0$  g/dL in any 2-week period or  $> 2.0$  g/dL in any 4-week period).
- Hb above 11.0 g/dL (US) or above 12 g/dL (Europe).
- New elevations in ALT or AST  $> 3x$  ULN, without elevation in total bilirubin.
- Vadadustat arm: ESA use.
- Darbepoetin alfa arm: ESA use other than darbepoetin alfa IMP.

While receiving ESA rescue, subjects must temporarily discontinue IMP. Unless contraindicated, treatment with IMP should be resumed within a 30-day time period from the start date of the interruption. Re-start of IMP should be assessed at every visit following IMP interruption.

If a subject is receiving a tolerated dose of IMP prior to interruption, the subject may interrupt IMP for a maximum duration of 30 days. Re-start of IMP should be assessed at every visit following IMP interruption. Prior to the end of the 30-day time period from the start date of interruption, the investigator, in consultation with the sponsor's Medical Monitor or CRO designee, should assess either if the subject can or cannot be re-started on the IMP. If by Day 30 the subject will not be re-starting IMP, they will be

permanently discontinued from the trial and will complete the ET Visit and the Safety Follow-up Visit assessments.

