### 7.3.2 Treatment Discontinuation

After treatment assignment, a subject may stop treatment permanently for a variety of reasons. Treatment discontinuations may be initiated by a subject who is not satisfied with treatment or may become medically necessary due to AEs, required treatment with a disallowed medication or therapy, or other issues, as determined by the investigator.

However, each investigator must comprehensively review the circumstances and offer the subject options for continued treatment to the degree possible. If, after discussion with the investigator about possible mitigations for AEs, etc., the subject still chooses to discontinue IMP, the subject will permanently discontinue IMP and will complete the ET Visit assessments and will complete the Safety Follow-Up Visit, 4 weeks after last dose of IMP and the subject will not be allowed to re-start the IMP.

Trial medication is to be permanently discontinued if ESA rescue (other than darbepoetin alfa in comparator arm, any ESA in vadadustat arm) is not in the setting of acute bleeding (ie, gastrointestinal bleed, surgery, excess bleeding) and one of the following:

- The first cycle of ESA rescue lasts >30 days or
- Subject requires a second cycle of ESA for rescue (that must be related to anemia) at any time.

Trial medication must be permanently discontinued if a subject meets one of the criteria in [Table 7.3.2-1](#).

Table 7.3.2-1 Trial Medication Stopping Rules	
ALT or AST > 3x ULN and total bilirubin > 2x ULN	Permanently Discontinue Treatment
ALT or AST > 3x ULN and INR > 1.5	Permanently Discontinue Treatment
ALT or AST > 8x ULN	Permanently Discontinue Treatment
ALT or AST remains > 5x ULN over 2 weeks a	Permanently Discontinue Treatment
ALT or AST > 3x ULN with symptoms including eg, fatigue, nausea, vomiting, right upper quadrant pain, fever, rash or eosinophilia	Permanently Discontinue Treatment

INR: international normalized ratio; ULN: upper limit of normal

aRe-challenge generally should be avoided with ALT or AST > 5x ULN unless there are no other good therapeutic options.

See [Section 8.8](#) for reporting requirements related to a subject being permanently discontinued based on meeting the laboratory abnormalities list above in [Table 7.3.2-1](#).

For subjects who permanently discontinue IMP, the investigator will resume standard of care treatment, including ESAs and iron therapy, as deemed appropriate.

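### Every listed table that includes ESA rescue counts large control-arm darbepoetin increases as rescue; add one version limited to non-study ESA, and state the base of the percentage

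*SAP*

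**What the plan says.** SAP 6.4 recognises the difficulty of defining rescue in the control arm. It notes that, "since the study drug itself is an ESA", "the increase dose in darbepoetin alfa may be planned titration or a rescue". It then decides by size alone: at either threshold (at least 50%, or at least 100%), "dose increases from last dose will be considered as rescue therapies". The rule sits in both rescue definitions. The narrow definition otherwise concerns worsening anaemia, with Hb below 9.5 g/dL as a listed reason. The broad-on-treatment definition first sets aside control-arm darbepoetin that is not designated as rescue. Neither says clearly that an increase must be tied to an Hb value or a recorded reason.

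SAP 9.4.5 and the table titles in SAP 19 carry the rule into the rescue analyses. SAP 9.2.5 uses the same definitions in the sensitivity analysis that sets Hb near rescue to missing and imputes it.

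For treatment conduct, the protocol draws a different line in the control arm. Section 7.3.2 refers to "ESA rescue (other than darbepoetin alfa in comparator arm, any ESA in vadadustat arm", and section 7.3.1 lists "Darbepoetin alfa arm: ESA use other than darbepoetin alfa IMP".

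The SAP does not say whether the last dose is per injection or per week, or prescribed or given. Protocol 4.1 says that "the dosing schedule may shift per local standard of care and investigator discretion", and Protocol 7.3.1 allows interruption for "Missed dialysis visit (darbepoetin alfa arm". Elsewhere in SAP 6.4, ESA doses "will be converted to IV epoetin equivalent units per kilogram per week (U/kg/week".

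**The concern.** The rule has a purpose: a control subject can be rescued by raising the study ESA, and ignoring that would undercount control rescue. But the SAP itself says the same increase may be titration, and counting all large increases works in one direction only. It adds control-arm rescue events and never vadadustat-arm events.

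If the rescue proportion or hazard ratio favours vadadustat, the reader will want to know whether controls needed another ESA or whether their darbepoetin was titrated. No planned between-arm estimate separates the two. SAP 5.3 and Table 14.1.7.4 (concomitant ESA use) and Tables 14.1.9.5.1 and 14.1.9.5.2 (maximum darbepoetin increase) give the components, but only descriptively.

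The open base of the percentage is a smaller, related matter. Two programmers could flag different subjects from the same dosing records.

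**Working it through.** **The plan's own figures.** The documents give no rescue or titration rate, so there is no figure on this point to reproduce. Their only design figure is power above 90% for the primary test. With 70 completers per arm (100 less 30%), SD 1.2 and margin 0.75, Φ(0.75 / (1.2·√(2/70)) − 1.96) = Φ(1.74) ≈ 95.9%. That agrees with the stated figure, and nothing below touches it.

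**Table count, from SAP 19.**

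| Analysis | Tables | Count |
|---|---|---|
| ESA-rescue proportion | 14.2.4.3.1.1 to 14.2.4.3.4.2 | 8 |
| Time to first ESA rescue | 14.2.4.4.1 to 14.2.4.4.4 | 4 |
| Time to ESA rescue or transfusion | 14.2.4.7.1 to 14.2.4.7.4 | 4 |
| Rescue-imputed Hb, Weeks 20–26 | 14.2.1.2.3.1–2, 14.2.1.2.4.1–2 | 4 |
| Rescue-imputed Hb, Weeks 46–52 | 14.2.2.2.3.1–2, 14.2.2.2.4.1–2 | 4 |
| **Tables using the rule** | | **24** |
| Transfusion only (rule not used) | 14.2.4.5.1.1–2, 14.2.4.5.2.1–2, 14.2.4.6.1–2 | 6 |

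So 24 of the 30 rescue-based tables use the rule, and none of the 24 has a counterpart without it.

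**What triggers the rule** (Protocol Table 6.1.1.2-1 gives a darbepoetin step of about 25%).
- One step up: +25%, not counted.
- Return from a 25% cut: 1/0.75 − 1 = +33.3%, not counted.
- Return in one step from a one-third cut: 1/(2/3) − 1 = +50%, counted. From a halving: 1/0.5 − 1 = +100%, counted.
- Two successive 25% steps: 1.25² − 1 = +56.25% in total, but neither step is counted, because each is compared with the last dose.

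**Size, with all rates assumed.** Take n = 100 per arm and the same true rescue rate r in both arms. A further k of 100 controls have only a counted increase. Then RD = r − (r + k/100) = −k/100, one percentage point per control subject. SE = √[r(1−r)/100 + c(1−c)/100] with c = r + k/100, and the Wald interval is RD ± 1.96·SE, unstratified. The first k at which the interval excludes zero:

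| r | k | RD (points) | 95% CI |
|---|---|---|---|
| 5% | 8 | −8 | −15.9 to −0.1 |
| 10% | 10 | −10 | −19.8 to −0.2 |
| 20% | 13 | −13 | −25.1 to −0.9 |

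At r = 10% and k = 9, SE is 4.94 points and the interval is −18.7 to +0.7. Under constant hazards and complete follow-up, the hazard ratio is ln(0.90)/ln(0.81) = 0.50, although true rescue is equal.

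**The opposite error.** A version that counts only non-study ESA can mislead the other way. If true rescue is 10% in both arms and half of the control rescue is given by raising darbepoetin, the control arm reads 5%. Then RD = +5.0 points (−2.3 to +12.3) and HR = ln(0.90)/ln(0.95) = 2.05. Neither version is a bound on the truth.

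**Base of the percentage, with assumed schedules.** Dose X weekly changed to 2X every 2 weeks is +100% per injection and 0% per week. Dose X every 2 weeks changed to X weekly is 0% per injection and +100% per week. If a held dose is entered as a last dose of zero, the percentage is undefined.

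**The case against.** The strongest reply is that titration is largely designed out. The lower threshold is twice the protocol's step of about 25%, increases are in general limited to one every 4 weeks, and reversing a one-step cut does not reach 50%. Two thresholds are reported, so the reader sees some sensitivity to the cut. This stands: a reader might infer that routine titration is being called rescue, and the documents do not support that. What remains exposed is larger single moves, such as a one-step return from a big reduction.

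Second, the components are visible. SAP 5.3 summarises concomitant ESA and reasons for use by arm, Tables 14.1.9.5.1 and 14.1.9.5.2 summarise the increases, and Listing 16.2.4.6.2 gives subject-level ESA use. A reader could approximate the missing count, but not its confidence interval, hazard ratio or effect on the Hb sensitivity analysis.

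Third, Protocol 7.3.1 and 7.3.2 are interruption and discontinuation rules, not endpoint definitions, and the SAP prevails where the two differ. That is right. They show that the sponsor already uses the distinction, not that the SAP contradicts the protocol endpoint.

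Fourth, the remark in Protocol 4.1 about a shifting schedule may mean only that dosing days need not match visits. No passage describes a switch from weekly to fortnightly dosing, so the interval example is an assumption. The undefined base does not depend on it.

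A reader might also infer that the four-week deletion in SAP 9.2.5 could run backwards from rescue. The preceding sentence there, on data that rescue may have affected, already points to a forward window, so this is not pressed.

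**Conclusion.** The point holds as a modest gap in the analysis set. The dose-increase rule has a legitimate purpose, but it is in all 24 tables that include ESA rescue. It can only add control-arm rescue events, and no between-arm estimate is planned without it. The 8 to 13 controls per 100 shown above rest on assumed equal true rescue of 5% to 20%, 100 per arm and an unstratified interval. The SAP will use a stratified Mantel-Haenszel estimate, and the actual size cannot be known from the documents.

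Two stronger conclusions are tempting and unsupported. One is that the rule threatens the noninferiority result. It does not: ESA rescue is absent from the eight-step hierarchy in SAP 9.5, and the primary analysis uses Hb regardless of rescue. The other is that the rule biases the rescue-imputed Hb analyses toward vadadustat. The direction there is uncertain, because it depends on which control Hb values are removed and what replaces them.

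**What to change.** 1. In SAP 6.4, 9.2.5, 9.4.5 and the table list, keep the 50% and 100% versions. Beside them add one version, on the broad-on-treatment definition, that counts only ESA other than study darbepoetin in every arm, plus transfusion where the analysis includes it. Apply it to the ESA-rescue proportion (randomized population and FAS, 2 tables), time to first ESA rescue (1), the composite with transfusion (1), and the rescue-imputed Hb analyses for Weeks 20–26 (1) and Weeks 46–52 (1): 6 tables. Report the versions together as complementary definitions, not bounds. State that the added version misses rescue given by raising darbepoetin, and that both miss rescue given by smaller increases.

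2. As an accompanying clarification, compute the percentage on prescribed weekly-equivalent darbepoetin dose (dose divided by interval in weeks), against the last non-zero prescribed weekly dose. An interval change at an unchanged weekly dose, or resumption at the prior dose after a held dose, then does not count. An interval change that raises the weekly dose still counts, as does a one-step return from a large prescribed cut; only item 1 shows the effect of the latter.

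The cost is SAP wording, six tables and one event-level derivation. ESA and transfusion reasons are already collected in the eCRF (SAP 6.4), and average weekly dosage is already summarised (SAP 4.1). Item 2 assumes the dosing eCRF records frequency or injection dates. Only derived variables change; how rescue or study drug is given does not.
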